2.3. Sample Size Calculation

In this study, the sample size was calculated based on the “The Scale for Dietary Behaviors in Hemodialysis Patients” used in a similar study (Düzalan & Pakyüz, 2018). A total of 70 individuals receiving hemodialysis treatment, 35 patients in each group, were included in the study based on a common type-I error rate of 0.05, the effect size rate of 0.80 and estimated loss to follow-up of 10%.

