2.6 The Intervention

The intervention group will received 15 minute motivational interviewing in four session once a month and one session face-to-face education with booklet at the first motivational interviewing based on Watson's Theory of Human Caring before the hemodialysis session in a separate room in the hemodialysis unit.

Motivational Interviewing: The semi-structured interview based on Watson's Theory of Human Caring according to the principles of motivational interviewing such as open-ended questions, affirmation, reflection, summaries and speaking change will perform. In the motivational interviewing sessions, the agenda will set for the individuals to talk about their current concerns about fluid intake, diet and drug management, and physical, psychological and social support problems. It will aimed to reveal the individuals' personnel goals to improve their adherence to treatment and the obstacles they perceived to achieve these goals. By working with the ambivalence of the individuals, supporting their optimism and self-efficacy and positive changes, individuals will enable to determine their own solutions. In addition, individuals will support for the maintaining of behavior change.

Education: The education will apply face-to-face in one session for 30 minutes in the first motivational interviewing and an education booklet will give to the participants. The education booklet has been prepared by the researcher, according to evidence-based guidelines, literature search and result of study (<https://rb.gy/nxkgf4>, Accessed date: 24.11.2017; <https://rb.gy/totnpp>, Accessed date: 27.11.2017). The education booklet was evaluated by 10 experts in the field of nephrology and hemodialysis according to Discern guide. The educational booklet includes sections on kidneys, kidney functions, causes, symptoms, stages and treatment of chronic kidney disease (CKD), nutrition in hemodialysis, fluid intake, drugs, hemodialysis related problems, laboratory parameters.

Conceptual-theoretical-empirical (C-T-E) system-based nursing practice was used in the study. The C-T-E structure provide a purposeful and systematic process for nursing practice (Fawcett, 2005).

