3. ANALYSIS

The data were analysed with the IBM Statistical Package for Social Science (SPSS) for Windows version 25 (IBM, 2017). The normality test was performed with the graphical assessment, skewness and kurtosis test. Descriptive statistics for normally distributed numerical variables were presented as mean, standard deviations, n (%) or minimum-maximum. While evaluating statistical significance, it was considered according to the p value of <0.05 .

Adherence to fluid intake, diet and drug management, physical parameters and quality of life will compare intervention groups (motivational interviewing and education based Watson's Theory of Human Caring vs control treatment) on their mean change between baseline and 12 weeks using independent sample t-test. In addition, effect size will evaluated by calculator for student's t-test using G-Power programme. To identify the relationship of the change adherence to fluid intake, diet and drug management, physical parameters and quality of life with other variables such as group and demographic variables will use multivariate linear regression.

Patiens satisfaction will analyzed using descriptive analysis such as n (%) or minimum-maximum.

References

Düzalan, Ö. B., & Pakyüz, S. Ç. (2018). Educational interventions for improved diet and fluid management in haemodialysis patients: An interventional study. *Journal of Pakistan Medical Association*, 68(4), 532-537.

Fawcett, J. (2005). Watson's Theory of Human Care. In J. Fawcett (Ed.), *Contemporary Nursing Knowledge an Analysis and Evaluation of Nursing Models and Theories* (pp. 553-599). Philadelphia: F.A. Davis Company.

IBM. (2017). SPSS version 25.0. New York: IBM Corporation.

Luyckx, V. A., Tonelli, M., & Stanifer, J. W. (2018). The global burden of kidney disease and the sustainable development goals. *Bulletin of the World Health Organization*, 96(6), 414-422. doi:10.2471%2FBLT.17.206441

Naalweh, K. S., Barakat, M. A., Sweileh, M. W., Al-Jabi, S. W., Sweileh, W. M., & Sa'ed, H. Z. (2017). Treatment adherence and perception in patients on maintenance hemodialysis: A cross-sectional study from Palestine. *BMC Nephrology*, 18(1), 178-186. doi:10.1186/s12882-017-0598-2

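### The change-score t-test can use only patients with a week-12 score, and the plan, which allows for 10% loss, does not say how patients who stop sessions are followed or analysed

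*Combined protocol and SAP*

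**What the plan says.** Section 3 (ANALYSIS) compares the two groups on fluid, diet and drug adherence, physical parameters and quality of life "on their mean change between baseline and 12 weeks using independent sample t-test". A multivariate linear regression then uses the same change variables as outcomes. For significance, "it was considered according to the p value of <0.05"; whether tests are one- or two-sided is not stated.

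Section 2.3 (Sample Size Calculation) gives "A total of 70 individuals receiving hemodialysis treatment, 35 patients in each group", based on a "common type-I error rate of 0.05", "the effect size rate of 0.80" and an "estimated loss to follow-up of 10"%. No power is stated.

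The Outcomes section (numbered 2.6, like the intervention section) schedules each between-group outcome at baseline and week 12 only, with no intermediate measurement.

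Section 2.6 The Intervention gives that arm "15 minute motivational interviewing in four session once a month", plus one education session at the first interview. These are held in the hemodialysis unit, before dialysis. Under Section 2.7 (Control Group), controls have routine care and one education session at week 12.

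The document defines no analysis population, does not mention intention-to-treat, gives no rule for missing data and plans no sensitivity analysis. It does not say whether a patient who stops the sessions is still measured at week 12.

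**The concern.** The plan expects loss and enlarges the sample for it, but it has no rule for handling it. Enlarging the sample protects power. It does nothing for the comparability of the patients who remain.

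Because each outcome has a single follow-up measurement, a patient without it contributes nothing to the t-test or to the regression on change. Eligibility selects patients with poor adherence, and adherence is the outcome, so a patient's reason for leaving could be related to the outcome. Before week 12 only the intervention arm has study sessions that a patient can stop attending. If patients who stop sessions also go unmeasured, the arms compared at week 12 may differ from the arms that were randomised, and the treatment estimate would carry a bias that a larger sample does not reduce.

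**Working it through.** **Inputs from the documents.** 70 patients, 35 per arm, and 10% loss (Section 2.3); two measurement times (Outcomes); t-test on change (Section 3). The deficit in lost patients and the split of losses between arms are not given, so both are assumed below and varied.

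**The plan's own figure.** Because no power is stated, 70 cannot be reproduced uniquely. Reading 0.80 as a standardised difference, with a two-sided 5% t-test and division by 0.90:
- 80% power: 26 per arm, 26/0.90 = 28.9, so 29 (58 in total)
- 85% power: 30 per arm, 30/0.90 = 33.3, so 34 (68 in total, close to 70)
- 90% power: 34 per arm, 34/0.90 = 37.8, so 38 (76 in total)

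The point does not depend on which of these was intended.

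**Expected loss.** 0.10 × 70 = 7, leaving 63 with a change score: 31 or 32 per arm if balanced, 28 v 35 if all losses are in the intervention arm.

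**Effect on power.** On the same reading of 0.80, two-sided power is 91.0% at 35 per arm, 87.3% at 31 per arm and 87.4% at 28 v 35. Power falls little, so what matters is bias.

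**Formula for bias.** Let lost patients change g SD less than retained patients in the same arm, and let L be the share of the arm lost. The retained mean then exceeds the mean of the whole arm by L × g. If g is the same in both arms, the bias in the difference is

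g × (L intervention − L control).

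If g differs between arms, the bias is g₁L₁ − g₂L₂, where 1 is the intervention arm and 2 the control arm.

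**Results for seven losses** (SD units of change; positive values favour the intervention):

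| Losses, intervention : control | g = 0.5 | g = 0.8 | g = 1.0 |
|---|---|---|---|
| 7:0 | 0.100 | 0.160 | 0.200 |
| 6:1 | 0.071 | 0.114 | 0.143 |
| 5:2 | 0.043 | 0.069 | 0.086 |
| Equal shares | 0 | 0 | 0 |
| 2:5 | −0.043 | −0.069 | −0.086 |
| 0:7 | −0.100 | −0.160 | −0.200 |

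For example, 7:0 with g = 0.8 gives 0.8 × 7/35 = 0.160. If lost patients did better than those retained, every sign would reverse.

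**Against the standard error.** At 31 per arm, √(2/31) = 0.254 SD. At 28 v 35, √(1/28 + 1/35) = 0.254 SD. The 7:0 biases are 0.39, 0.63 and 0.79 of a standard error. At 5:2 with g = 0.8 the ratio is 0.069/0.254 = 0.27.

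**Type I error.** This was simulated with no true effect, normal data with SD 1, 40,000 runs and a two-sided 5% test. With seven losses, all in the intervention arm, the rejection rate was 4.8% at g = 0, 6.6% at 0.5, 9.7% at 0.8 and 12.0% at 1.0. With three losses, all in that arm, it was 5.0%, 5.4%, 5.9% and 6.2%.

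**The case against.** The strongest reply is that the plan is silent, and silence is not a decision to exclude. Nothing removes or reassigns a patient who stops the sessions. The Outcomes section schedules week-12 measurement without any condition on attendance, and Section 3 makes no per-protocol exclusion. Stopping sessions is also not the same as missing the week-12 measurement. The sessions take place at dialysis visits, so a patient who declines them but still dialyses in the unit can be measured. Patients who are truly lost may be those who leave the unit, which can happen in either arm.

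All of that stands, and it rules out two stronger readings that a reader might infer. One is that the sponsor chose to analyse completers only. The documents do not say so; a complete-case comparison is what the stated methods give when no other rule is written. The other is that loss will fall mainly on the intervention arm and inflate its result. No section gives loss by arm or reasons for loss, and the same formula gives zero or reversed bias under equally admissible assumptions. Controls also have one study session, although at week 12 it gives no reason to leave earlier.

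It is also fair to say that a heavy remedy would not suit this trial. Imputing from many baseline variables with about 28 to 35 patients per arm risks overfitting. Imputation under missing-at-random does not by itself remove bias from loss that depends on the unseen outcome.

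What remains is that a change score cannot be formed without a week-12 value, that loss is expected, and that no rule covers it.

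**Conclusion.** The point holds as an unaddressed default. The stated t-test and the regression on change can use only patients with a week-12 score, about 7 of 70 may lack one, and the plan does not commit to measuring patients who stop sessions or to keeping them in their assigned arm.

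The documents settle neither the size nor the direction of any bias. With seven losses and a common deficit of 0.5 to 1.0 SD, the bias lies between −0.20 and +0.20 SD, and it is zero when loss and deficit match across arms. The upper end needs all seven losses in one arm. At 7:0 with a 0.8 SD deficit, it is 0.16/0.80 = one fifth of the stated effect size, if 0.80 is a standardised difference in change. The deficits and splits are assumptions. Because the direction cannot be known in advance, the rule should be written before the data are seen by arm.

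**What to change.** 1. **Follow-up and analysis set.** State that week-12 scales and bloods will be collected from every randomised patient still dialysing in the unit, whatever number of sessions was attended, and that each is analysed in the assigned arm.
2. **Main analysis.** Replace the t-test on change with a linear model of the week-12 score on arm and baseline score. It uses data already collected and is generally more precise. It also omits patients without a week-12 score, so it complements item 1 and does not replace items 1 and 3.
3. **Missing data.** Report the number lost and the reasons by arm. Add one simple sensitivity analysis for missing week-12 scores on the adherence scales, for example multiple imputation from a small set of baseline variables with a delta shift applied to either arm. The shift examines loss that depends on the unseen outcome, and applying it to either arm avoids presuming a direction.

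**Cost.** A short addition to the SAP, modest extra analysis, and some effort to collect week-12 data from patients who have stopped the sessions. The estimate may be slightly less favourable once those patients are included. If data collection has finished, the analysis set, the model, the reporting of loss and the sensitivity analysis can still be specified.
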